When a subject has an existing symptom that is transient (e.g., asthma, epilepsy) and incidence of the symptom is increased, or the symptom becomes serious or severe, it should be recorded as an adverse event. When a subject has a chronic disease (e.g., cataract, rheumatoid arthritis) and the symptom is aggravated more than anticipated, it should be recorded as an adverse event. The investigator or the subinvestigator should record in a way that will make the reported adverse event name be recognized as a change from baseline (e.g., aggravation of XX).

Change of severity of adverse events:

When the severity of an adverse event has changed, the event should be recorded once at the highest degree of severity (grade based on the CTCAE [Japanese edition JCOG version 4.03]), and should be recorded in each protocol treatment course.

Previously planned surgery or treatment:

Surgery or treatment planned before initiation of protocol treatment is not considered an adverse event. However, when the existing symptom is aggravated to require emergency surgery or treatment, the condition or the event is considered an adverse event. A complication which resulted from previously planned surgery is reported as an adverse event.

Non-urgent surgery or treatment:

Non-urgent surgery or treatment that does not induce a change in the condition of a subject (cosmetic surgery, etc.) is not considered an adverse event. However it should be recorded in the source documents. Complications due to a non-urgent surgery should be reported as an adverse event.

Progressive Disease (PD):

PD should be considered lack of efficacy, not an adverse event. In addition, the single fact of PD does not necessarily constitute a serious adverse event. However, if a clinical or on imaging progression of pre-existing cancer (including new metastasis) is confirmed, it will be determined as a serious adverse event if the severity satisfies any of the criteria specified in Section 10.1.3.

Panitumumab overdose:

When overdose of panitumumab becomes apparent, it should be recorded in the CRF. If adverse event occurs with overdose, it should be recorded as an adverse event in the adverse event column of the CRF.

Furthermore, the overdose of panitumumab is defined as follows.

- 1) Received administration exceeding approved dosage (6 mg/kg) of panitumumab
- 2) Received next administration within 10 days of previous administration

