7.2.5 Safety analysis

The following analyses regarding TEAEs will be performed on the “full analysis set” and “safety analysis set.”

TEAEs will be coded using MedDRA and summarized by SOC and PTs.

A subject with multiple events in the same SOC will be counted once for that SOC. A subject with multiple events with the same PT will be counted once for that PT.

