7.2.5.12 Frequency tabulation of non-serious TEAEs with > 5% incidence

- 7.2.5.13 Frequency tabulation of non-serious TEAEs with $> 5\%$ for which the causal relationship with protocol treatment was “related”
- 7.2.5.14 Frequency tabulation of non-serious TEAEs with $> 5\%$ for which the causal relationship with panitumumab was “related”
- 7.2.5.15 Frequency tabulation of TEAEs with \geq Grade 3
- 7.2.5.16 Frequency tabulation of TEAEs with \geq Grade 3 for which the causal relationship with protocol treatment was “related”
- 7.2.5.17 Frequency tabulation of TEAEs with \geq Grade 3 for which the causal relationship with panitumumab was “related”
- 7.2.5.18 The incidence rate of TEAEs with \geq Grade 3
- 7.2.5.19 The incidence rate of TEAEs with \geq Grade 3 for which the causal relationship with protocol treatment was “related”
- 7.2.5.20 The incidence rate of TEAEs with \geq Grade 3 for which the causal relationship with panitumumab was “related”

The following analyses will be performed on the “full analysis set” and “safety analysis set”:

The worst grade in each subject will be calculated. The incidence rate of TEAEs of Grade ≥ 3 and the 95% confidence intervals using Agresti-Coull methods will be calculated. Similarly, incidence rate and the 95% confidence interval of TEAEs will be calculated in the number of TEAE incidence with \geq Grade 3 as the numerator, and the TEAE collecting periods as the denominator. The 95% confidence intervals will be calculated using the following formula:

$$\text{The 95\% confidence intervals of incidence rate} = \text{incidence rate} \pm 1.96 \sqrt{\frac{\text{incidence rate}}{\text{TEAE collecting period}}}$$

Skin toxicity will be analyzed similarly as described above (7.2.5.1 to 7.2.5.20)

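### The person-time rate of Grade 3 or higher TEAEs does not say whether it counts subjects or events, and its prescribed denominator and interval do not fit either count without change

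*SAP*

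**What the plan says.** SAP v4.0 7.2.5.18 to 7.2.5.20 lists incidence rates of TEAEs of Grade 3 or higher: all, those related to protocol treatment, and those related to panitumumab. The same set is repeated for skin toxicity. The accompanying text describes two quantities.

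- The first is at subject level. "The worst grade in each subject will be calculated", and for the resulting incidence "the 95% confidence intervals using Agresti-Coull methods will be calculated".
- The second is a person-time rate. The SAP says that "the 95% confidence interval of TEAEs will be calculated in the number of TEAE incidence" of Grade 3 or higher "as the numerator, and the TEAE collecting periods as the denominator". "The 95% confidence intervals will be calculated using the following formula": rate ± 1.96 × √(rate / TEAE collecting period).

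SAP 6.3.3.18 to 6.3.3.20 repeats this for phase I, and section 13.3.4.1 of the amended protocol carries the same method.

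Four other provisions bear on what is counted and over what time.

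- Protocol 10.1.2, on change of severity, has an event entered once at its highest grade, "and should be recorded in each protocol treatment course". Protocol 10.2.1.2 asks for outcome and resolution date for the last course.
- SAP 4.1(2) reports the highest grade when an AE is assessed several times in a subject.
- SAP 7.2.5 states: "A subject with multiple events with the same PT will be counted once for that PT".
- Protocol 10.2.1.1 ends routine collection 28 days after discontinuation, or at the start of follow-up treatment if earlier, but has related events collected after that as well.

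**The concern.** A person-time rate needs a counting unit, a matching time at risk and a variance that suits both. Here the unit is not named, so two programmers could follow the SAP and report different rates.

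If the unit is the event, the formula gives every event Poisson variance, as if several events in one patient were unrelated. Toxicity usually clusters in susceptible patients, so the interval would be too short. Course-by-course entry adds a second risk: one continuing event may appear as several records. If the unit is the subject, the denominator still includes time after a subject's first event, when that subject can no longer add to the count.

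At stake is the description of severe toxicity per unit of time for the combination, overall and for skin, in a single-arm study whose phase II objective includes safety.

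**Working it through.** The plan states no rate, event count or interval for this analysis, so there is no figure to reproduce. The check concerns the formula under each reading.

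**Formula.** With d events in total time T, rate = d/T and √(rate/T) = √d / T. This is the Poisson Wald interval, and 1.96 is right for two-sided 95%. For independent events its exact coverage is 0.949 at 52 expected events, 0.933 at 36, 0.926 at 10 and 0.87 at 5. The algebra is sound; the question is what is put into it.

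**Inputs for illustration.**
- 52 subjects (Protocol 6.1).
- Treatment for 6 months as a guide (Protocol 2.0) plus 28 days: 6 + 28/30.4375 = 6.92 months each, or 359.8 person-months in all. Equal follow-up is assumed.
- 68% affected: Grade 3 neutropenia 56% + Grade 4 12% in the cited TAS-102 plus bevacizumab study (Protocol 4.1.4.2). This is a different combination, so other proportions are shown too.
- Between-subject heterogeneity (gamma frailty variance φ) and records per episode (m) are assumptions. The documents give neither.

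**Reading 1: distinct events over total time.** The point estimate is a valid mean event rate. With mean μ events per subject, the variance is 1 + μφ times Poisson. Simulated coverage of the stated interval (52 subjects, 20,000 runs):
- μ = 1: 0.89, 0.84 and 0.74 for φ = 0.5, 1 and 2.
- μ = 2: 0.85, 0.75 and 0.63 for φ = 0.5, 1 and 2.
- φ = 0: about 0.95 for either μ.

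As a check, the approximation 2Φ(1.96/√(1 + μφ)) − 1 gives 0.742 for μ = 2, φ = 1, against 0.753 simulated.

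**Reading 2: course records over total time.** If each episode is entered m times, the rate is multiplied by m and the standard error is understated by √m, even with independent episodes. Coverage of the inflated mean is 2Φ(1.96/√m) − 1: 0.89, 0.83 and 0.74 for m = 1.5, 2 and 3.

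**Reading 3: subjects over uncut time.** Under a constant hazard with a proportion p affected, the computed ratio divided by the first-event rate is p / −ln(1 − p):
- p = 10%: 0.95
- p = 30%: 0.84
- p = 50%: 0.72
- p = 68%: 0.60
- p = 80%: 0.50

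With 35 of 52 affected (0.68 × 52 = 35.4, rounded), the plan's ratio is 35/359.8 = 9.7 per 100 person-months (95% CI 6.5 to 12.9). The first-event rate is −ln(1 − 35/52)/6.92 = 16.2 per 100 person-months (10.8 to 21.5), on 216.6 person-months at risk.

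For the ratio actually computed, the stated interval is 1/√(1 − p) times the binomial width: 1.41 at 50% and 1.77 at 68%. Its exact coverage is 0.90, 0.97, 0.99 and 0.998 at p = 10%, 30%, 50% and 68%.

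**Time window.** Related events collected after the period in Protocol 10.2.1.1 could enter the numerator with no matching time in the denominator.

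**The case against.** A reader might infer that the rate and its interval are wrong however the numerator is read. The documents do not support that. Distinct events over total collecting time is a valid mean rate, and only its interval is in doubt. When each subject counts once, the independence objection falls away and the interval is mostly conservative. The shortfall in the rate exists only against a first-event rate, which the SAP does not say it is estimating.

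A reader might also infer that every course record is counted as a new event. That is not established. Protocol 10.1.2 says in the same sentence that the event is entered once at its highest grade, and SAP 4.1(2) and the count-once rule at the head of SAP 7.2.5 both point towards collapsing. If each course carries its own highest grade, a Grade 3 event that continues at a lower grade adds no further Grade 3 record. The criteria for starting a course (Protocol Tables 8.d and 8.e) also make an unbroken Grade 3 event over many courses less likely, although Protocol 8.4 allows one drug to continue alone. These points stand. They leave record inflation as a possibility, because none of these rules is expressly applied to the person-time numerator. The count-once rule also works per PT, so a subject could still contribute several PTs to an overall rate.

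Nor are these the only safety results that account for time or exposure. SAP 7.2.3.3 analyses stomatitis against cumulative dose by Kaplan-Meier, and SAP 7.2.6.3 gives days to onset for selected events.

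Finally, the output is descriptive and feeds no decision rule. That limits the consequence but does not supply the missing definition.

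**Conclusion.** The concern holds in this form: the counting unit is undefined, time is not cut at the first event, and the prescribed interval assumes independent events.

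- If events are counted, the interval is too narrow whenever events cluster within subjects. Coverage of about 0.85 to 0.63 rests on an assumed 2 events per subject and frailty variance of 0.5 to 2. The direction is secure; the size is not fixed by the documents. Re-entry across courses could raise the rate as well.
- If subjects are counted, the ratio is about 0.72 of the first-event rate at 50% affected and 0.60 at 68%, assuming a constant hazard and equal follow-up. The interval is then mostly conservative, with coverage of 0.90 at 10% affected as the exception.

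The primary test and the subject-level Agresti-Coull proportions are untouched. Exact Poisson limits would not settle the matter, since they repair neither clustering nor the denominator. The change is worth making because a stated interval rule can give misleading error bars and the remedy is inexpensive.

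**What to change.** In SAP 7.2.5.18 to 7.2.5.20 and 6.3.3.18 to 6.3.3.20, and in Protocol 13.3.4.1, replace the person-time text with the following.

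- **(a) First-event rate.** Subjects with a first Grade 3 or higher TEAE, divided by the sum of each subject's time to that event or to the end of the collecting period. The existing formula can serve here if its period is this time at risk.
- **(b) Event rate, if wanted.** Distinct Grade 3 or higher episodes over total collecting time. Merge course records of the same PT only when the event continued without resolution or recovery below Grade 3 between them. Merging all consecutive records would wrongly join separate recurrences, since a normal restart of TAS-102 requires recovery under Table 8.e. Use a subject-clustered 95% interval (robust variance or bootstrap over subjects) in place of the stated formula.
- For both, count only events that fall within the collecting period, and list later related events separately.

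The cost is SAP wording, a little more programming and wider intervals for (b). No new data collection is proposed. Because the resolution date is asked for in the last course, recovery between courses may have to be derived from laboratory values or course start dates, and the SAP should say how.

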7.2.6 Other safety analysis items

7.2.6.1 ECOG P.S.

The frequency distribution of ECOG P.S. in the “full analysis set” and “safety analysis set” will be tabulated for each course, and the percentage (%) will be indicated with the analysis set at Day 1 of each course (excluding withdrawal cases) as the denominator.

7.2.6.2 Laboratory tests

A shift table will be prepared by performing a cross tabulation (number of cases and the percentages) of the results of CTCAE grading based on laboratory values for each test item in the “full analysis set” and “safety analysis set,” using the worst grade at the start and after the start of treatment. The percentage (%) will be indicated with the respective analysis set as the denominator.

Test items:

Neutrophil count, platelet count, hemoglobin level, total bilirubin, ALT (GPT), AST (GOT), creatinine, Mg, albumin, Na, K, Ca

7.2.6.3 Number of days to the onset of specific event

Summary statistics will be calculated for the number of days from the start date of protocol treatment to the onset of the events below in the “full analysis set” and “safety analysis set.”

Target events:

≥ Grade 1 stomatitis, worst Grade stomatitis, ≥ Grade 3 stomatitis, ≥ Grade 3 dermatitis acneiform,
≥ Grade 3 hypomagnesaemia, ≥ Grade 2 skin toxicity

7.2.6.4 Subsequencet therapy

With regard to the implementation status of Subsequencet therapy in the “full analysis set” and “safety analysis set,” the frequency distribution of the following items will be shown, as well as the percentages (%) with analysis set as the denominator:

Implementation status of Subsequencet therapy

No	Patients with continuous treatment
	Deaths within 4 weeks of discontinuation of protocol treatment
	BSC after 4 weeks of discontinuation of protocol treatment
Yes	Regorafenib
	Other

7.2.6.5 Effects between specific events

Cross-tabulation by the presence/absence of occurrence and cross-tabulation by grade will be performed for events 1 and 2, below, in the “full analysis set” and “safety analysis set.” Cases of no event will be counted as Grade 0. The percentages (%) will be shown with analysis set as the denominator.

Event 1	Event 2
Neutropenia	Stomatitis
Dermatitis acneiform	Stomatitis

7.2.7 Table listing

The following tables will be created for the “enrolled subjects” in section 7.2.7.2 and for the “safety analysis set” in other sections

7.2.7.1 List of subjects who discontinued protocol treatment

Display items:

Subject No., enrollment phase, DLT evaluation set, full analysis set, safety analysis set, sex, age (years), start date of protocol treatment, date of discontinuation, reason for discontinuation, adverse event name (event name recorded by physician, LLT code, LLT (English, Japanese), PT code, PT English, Japanese), SOC code, SOC (English, Japanese), date of onset, severity, causal relationship of adverse event with protocol treatment, causal relationship with panitumumab, seriousness, discontinuation of protocol treatment, outcome, date of resolution

7.2.7.2 List of subjects/data excluded from analysis

Display items:

Subject No., enrollment phase, DLT evaluation set, full analysis set, safety analysis set, sex, age (years), start date of protocol treatment, reason for exclusion

7.2.7.3 List of fatal cases

Display items:

Subject No., enrollment phase, DLT evaluation set, full analysis set, safety analysis set, sex, age (years), start date of protocol treatment, date of death, reason for death, adverse event name (event name recorded by physician, LLT code, LLT (English, Japanese), PT code, PT (English, Japanese), SOC code, SOC (English, Japanese), date of onset, seriousness, causal relationship of adverse event with protocol treatment, causal relationship with panitumumab, seriousness, discontinuation of protocol treatment, outcome, date of resolution

7.2.7.4 List of treatments

Display items:

Subject No., enrollment phase, DLT evaluation set, full analysis set, safety analysis set, sex, age (years), start date of protocol treatment, primary lesion (information on primary organ, site, with/without resection, date of surgery), metastatic lesion (number of organs with metastases, site, with/without resection, date of surgery), performing a palliative colostomy (with/without, date of surgery), bypass surgery (with/without, date of surgery), radiation therapy (radical irradiation) (with/without, date of surgery, date of final dose), first-line treatment (start date, treatment details), second-line treatment (treatment details), third-line treatment (with/without, treatment details), preoperative/postoperative adjuvant chemotherapy (with/without, time period, oxaliplatin-containing regimen, date of final dose)

7.2.7.5 List of protocol treatment status

Display items:

Subject No., enrollment phase, DLT evaluation set, full analysis set, safety analysis set, sex, age (years), start date of protocol treatment, start date of TAS-102 by course, dose, number of doses, date of panitumumab administration, dose, presence or absence of discontinuation of protocol treatment, date of discontinuation, reason for discontinuation

7.2.7.6 List of complications

Display items:

Subject No., enrollment phase, DLT evaluation set, full analysis set, safety analysis set, sex, age (years), start date of protocol treatment, name of complication (name of complication recorded by physician, LLT code, LLT (English, Japanese), PT code, PT (English, Japanese), SOC code, SOC (English, Japanese)

7.2.7.7 Table of MedDRA-coded AEs

Display items:

Name of AE recorded by physician LLT code, LLT (English, Japanese), PT code, PT (English, Japanese), SOC code, SOC (English, Japanese)

7.2.7.8 List of TEAEs

Display items:

Subject No., enrollment phase, DLT evaluation set, full analysis set, safety analysis set, sex, age (years), start date of protocol treatment, adverse event name (event name recorded by physician, LLT code, LLT (English, Japanese), PT code, PT (English, Japanese), SOC code, SOC (English, Japanese), date of onset, severity, causal relationship with protocol treatment, causal relationship with panitumumab, seriousness, discontinuation of protocol treatment, outcome, date of resolution.

7.2.7.9 List of Deaths and other serious adverse events

Display items:

Same as "List of TEAEs"

7.2.7.10 List of skin toxicity

Display items:

Same as "List of TEAEs"

7.2.7.11 List of RECIST response evaluations

Display items:

Subject No., enrollment phase, DLT evaluation set, full analysis set, safety analysis set, sex, age (years), start date of protocol treatment, evaluation period, sum of target lesion diameter (before treatment, at evaluation), reduction rate of sum of target lesion diameter, results of response evaluation of target lesion, results of response evaluation of non-target lesion, development of new lesion, site of new lesion, results of overall response evaluation

$$\text{Reduction ratio of SoD} = \frac{\text{SoD at evaluation point} - \text{SoD before treatment}}{\text{SoD before treatment}} \times 100\%$$

7.2.7.12 List of determinations of PD

Display items:

Subject No., enrollment phase, DLT evaluation set, full analysis set, safety analysis set, sex, age (years), start date of protocol treatment, day of decision on clinical PD, day of decision on radiological PD, final day of imaging test, final day on which progression-free survival is confirmed, start date of follow-up treatment

7.2.7.13 List of survival survey results

Display items:

Subject No., enrollment phase, DLT evaluation set, full analysis set, safety analysis set, sex, age (years), start date of protocol treatment, survival survey results, last confirmed date of survival, date of death, reason of death (other details)

7.2.7.14 List of laboratory test values

Display items:

Subject No., enrollment phase, DLT evaluation set, full analysis set, safety analysis set, sex, age (years), start date of protocol treatment, laboratory test items, test date, measured values (SI), Unit (SI), site reference values (SI) (lower limit – upper limit)

Test items: Same as 7.2.6.2.

7.3 Criteria for interim analysis and premature discontinuation

No interim analyses are scheduled.

7.4 Sensitivity analysis

Sensitivity analysis of primary endpoint

For the PFS rate at 6 months (the primary endpoint), results will be calculated for the case in which the period is terminated at the point follow-up treatment is initiated, and the difference between major analysis results will be confirmed.

Kaplan-Meier method will be used to illustrate survival curve until the onset of event in the “full analysis set,” and the point estimation value of survival rate and its 95% confidence interval (two-sided) will be calculated at the quartile of PFS and specified time points. The Log-Log conversion of Brookmeyer and Crowley will be used to calculate the 95% confidence intervals of the quartiles for PFS.

In evaluating PFS, results will be calculated for the case of termination at the point follow-up treatment is initiated (start date of follow-up treatment), and the difference between that and the results for the case in which the period is cut off on the last confirmed date of progression-free status.

8. References

APOLLON study

(A phase I/II study for the safety and efficacy of Panitumumab in combination with TAS-102 for patients with *RAS* wild-type metastatic colorectal cancer refractory to standard chemotherapy)

(Protocol number: Panitumumab-1501)

Statistics Analysis Plan

Version 3.0

[figure not shown]

Table of Contents

1. History of preparation and revision	3
2. Analysis Plan Objectives	4
3. Time period for Analysis	4
4. Analysis data set.....	5
4.1 Handling of cases/data.....	5
4.2 Number of significant figures in analysis results.....	5
5. Software used for analysis.....	6
6. Statistical analysis of the phase I part of the study	7
6.1 Analysis set	7
6.2 Analysis of demographic and other baseline characteristics	7
6.3 Safety analysis	8
6.3.1 Incidence of DLT events with panitumumab + TAS-102 combination therapy	8
6.3.2 Listing of DLT events	8
6.3.3 Frequency tabulation of adverse events	8
7. Statistical analysis of the phase II part of the study.....	10
7.1 Analysis set	10
7.2 Evaluation of analysis set	10
7.2.1 Eligibility and analysis set.....	10
7.2.2 Analysis of demographic and other baseline characteristics.....	10
7.2.3 Medication status.....	11
7.2.4 Efficacy analysis.....	12
7.2.5 Safety analysis.....	16
7.2.6 Other safety analysis items	18
7.2.7 Table listing	18
7.3 Criteria for interim analysis and premature discontinuation	21
7.4 Sensitivity analysis.....	21
8. References	22

[figure not shown]
1. History of preparation and revision

Version	Date of approval	Author	Reason for revision
1.0	June 3, 2016	PPD ██████████	Not applicable, because it is the first version
2.0	February 28, 2017	PPD ██████████	(1) Addition of definition of protocol treatment and acceptable range (2) Addition of analysis plan for phase II part
3.0	December 28, 2017	PPD ██████████	(1) Addition of analysis items associated with the protocol revision (ver. 2.0) (2) 7.2.3 Completion of administration (3) 7.2.3.3 Dose reduction status

2. Analysis Plan Objectives

This analysis plan specifies how the initial and final analyses of the clinical study are planned to be conducted in accordance with the “Clinical Study Protocol of A phase I/II study for the safety and efficacy of Panitumumab in combination with TAS-102 for patients with RAS wild-type metastatic colorectal cancer refractory to standard chemotherapy” (hereinafter, protocol).

The study design is shown below.

3. Time period for Analysis

Phase I part: Analysis will be performed after completion of enrollment for phase I part and after completion of Dose Limiting Toxicity (DLT) evaluation period for all enrolled subjects, and when DLT has been evaluated.

Phase II part: Analysis will be performed after completion of enrollment for phase II part and when evaluation has been performed in all the enrolled subjects at 6 months after the start of protocol treatment (initial analysis) and at completion of period for all observations (final analysis).

Protocol treatment

With protocol treatment, in principle, combination therapy with panitumumab and TAS-102 will be conducted, and even if any of the criteria for suspension or discontinuation of either drug is met, treatment with other drugs will be continued unless any of the criteria for discontinuation of protocol treatment is met (Section 8.7 of protocol). Protocol treatment in principle will be initiated within 14 days of entry.

4. Analysis data set

